### 5.2.1 Nivolumab Dose Selection/Modification

#### 5.2.1.1 Nivolumab dose selection

Rationale is provided in **Section 4.2.1 – Rationale for Dose Selection/Regimen/Modification: Nivolumab**.

#### 5.2.1.2 Nivolumab dose modification

Nivolumab will be withheld for drug-related Grade 4 hematologic toxicities, non-hematological toxicity  $\geq$  Grade 3 including laboratory abnormalities, and severe or life-threatening AEs as per **Table 5.2.1.2-1** below.

**Table 5.2.1.2-1: Dose Modification Guidelines for Drug-related Adverse Events.**

Toxicity	Hold Treatment For Grade	Timing for Restarting Treatment	Treatment Discontinuation
Diarrhea/Colitis	2-3	Toxicity resolves to Grade 0-1	Toxicity does not resolve within 12 weeks of last dose or inability to reduce corticosteroid to 10 mg or less of prednisone or equivalent per day within 12 weeks
	4	Permanently discontinue	Permanently discontinue
AST, ALT, or Increased Bilirubin	2	Toxicity resolves to Grade 0-1	Toxicity does not resolve within 12 weeks of last dose
	3-4	Permanently discontinue (see exception below) a	Permanently discontinue
Type 1 diabetes mellitus (if new onset) or Hyperglycemia	T1DM or 3-4	Hold nivolumab and CMP-001 for new onset Type 1 diabetes mellitus or Grade 3-4 hyperglycemia associated with evidence of beta cell failure	Resume nivolumab when patients are clinically and metabolically stable
Hypophysitis	2-4	Toxicity resolves to Grade 0-1. Therapy with nivolumab and CMP-001 can be continued while endocrine replacement therapy is instituted	Toxicity does not resolve within 12 weeks of last dose or inability to reduce corticosteroid to 10 mg or less of prednisone or equivalent per day within 12 weeks
Hyperthyroidism	3	Toxicity resolves to Grade 0-1	Toxicity does not resolve within 12 weeks of last dose or inability to reduce corticosteroid to 10 mg or less of prednisone or equivalent per day within 12 weeks
	4	Permanently discontinue	Permanently discontinue
Hypothyroidism		Therapy with nivolumab and CMP-001 can be continued while thyroid replacement therapy is instituted	Therapy with nivolumab can be continued while thyroid replacement therapy is instituted
Infusion Reaction	2 b	Toxicity resolves to Grade 0-1	Permanently discontinue if toxicity develops despite adequate premedication
	3-4	Permanently discontinue	Permanently discontinue
Pneumonitis	2	Toxicity resolves to Grade 0-1	Toxicity does not resolve within 12 weeks of last dose or inability to reduce corticosteroid to 10 mg or less of prednisone or equivalent per day within 12 weeks Permanently discontinue for recurrent Grade 2 pneumonitis
	3-4	Permanently discontinue	Permanently discontinue
Renal Failure or Nephritis	2	Toxicity resolves to Grade 0-1	Toxicity does not resolve within 12 weeks of last dose or inability to reduce corticosteroid to 10 mg or less of prednisone or equivalent per day within 12 weeks
	3-4	Permanently discontinue	Permanently discontinue
All Other Drug-Related Toxicity c	3 Severe or	Toxicity resolves to Grade 0-1	Toxicity does not resolve within 12 weeks of last dose or inability to reduce corticosteroid to 10 mg or less of prednisone or equivalent per day within 12 weeks. Exceptions may be sought for neuropathy or other AE following discussion with Principle Investigator.
	4	Permanently discontinue	Permanently discontinue

**Note: Permanently discontinue for any severe or Grade 3 drug-related AE that recurs or any life-threatening event.**

a For patients with liver metastasis who begin treatment with Grade 2 AST or ALT, if AST or ALT increases by greater than or equal to 50% relative to baseline and lasts for at least 1 week then patients should be discontinued.

b If symptoms resolve within one hour of stopping drug infusion, the infusion may be restarted at 50% of the original infusion rate (e.g., from 100 mL/hr to 50 mL/hr). Otherwise dosing will be held until symptoms resolve and the subject should be premedicated for the next scheduled dose.

c Patients with intolerable or persistent Grade 2 drug-related AE may hold study medication at physician discretion. Permanently discontinue study drug for persistent Grade 2 adverse reactions for which treatment with study drug has been held, that do not recover to Grade 0-1 within 12 weeks of the last dose.

In case toxicity does not resolve to Grade 0-1 within 12 weeks after last infusion, trial treatment should be discontinued after consultation with the Sponsor. With investigator and Sponsor agreement, subjects with a laboratory adverse event still at Grade 2 after 12 weeks may continue treatment in the trial only if asymptomatic and controlled. For information on the management of adverse events, see **Section 5.6.1**.

Subjects who experience a recurrence of the same severe or life-threatening event at the same grade or greater with re-challenge of nivolumab should be discontinued from trial treatment.

### **5.2.1.3 Nivolumab timing of dose administration**

Trial treatment should be administered after all procedures/assessments have been completed as detailed on the Trial Flow Chart in **Section 6.0**. Trial treatment may be administered up to +/- 2 days before or after the scheduled Day 1 due to administrative reasons.

All trial treatments will be administered on an outpatient basis.

Nivolumab will be administered as a 30 minute IV infusion (treatment intervals may be increased due to toxicity as described). Sites should make every effort to target infusion timing to be as close to 30 minutes as possible. However, given the variability of infusion pumps from site to site, a window of -5 minutes and +10 minutes is permitted (i.e., infusion time is 30 minutes: -5 min/+10 min).

The Procedures Manual contains specific instructions for nivolumab dose calculation, reconstitution, preparation of the infusion fluid, and administration.

### **5.2.1.4 Nivolumab duration of administration**

During the Prime Phase (Weeks 1-7), nivolumab 240mg will be administered every 2 weeks (W2D1, W4D1, W6D1). During this period, missed doses will not be made up.

During the Boost Phase (Weeks 12-56), nivolumab will be administered at either 240mg every 2 weeks or 480mg every 4 weeks. 12 doses (if Q4W) or 23 doses (if Q2W) of nivolumab will be administered over this period. During this period, missed doses will be made up. The choice of Q2W versus Q4W administration of nivolumab will be physician dependent.

## **5.2.2 CMP-001 Dose Selection/Modification**

During the Prime Phase, the first dose of CMP-001 (week 1) is fixed at 5mg subcutaneously. Subsequent doses of CMP-001 administered during the Prime Phase (weeks 2-7) will be at 10mg administered intra-tumorally. Should patients develop side effects, intra-tumoral doses during this period of the Prime Phase (weeks 2-7) may be reduced (see **Table 5.2.2.3-1**).

Following resection, during the Boost Phase, the CMP-001 dose is fixed at 5mg injected subcutaneously at the site of the resected tumor.

Rationale for dose selection is provided in **Section 4.2.2 – Rationale for Dose Selection/Regimen/Modification: CMP-001**.

### **5.2.2.1 Recommended prophylaxis**

To reduce the severity of symptoms associated with CMP-001 induced cytokines, prophylaxis is strongly recommended. Prophylactic regimens already in place at institutions should be followed, if not, below is a suggested regimen that has been effective for the treatment of CMP-001 induced adverse events:

- Fluids (e.g. 1000 cc IV normal saline)
- NSAIDS (e.g. 1000 mg acetaminophen and 50 mg Indomethacin)
- Anti-emetics (e.g. 8 mg Zofran PO)
- Hydrocortisone prophylaxis (50-100mg hydrocortisone – only for patients with prior G2-3 CRS-like reaction)

If an Investigator incorporates prophylaxis, administration should occur 30 minutes prior to intra-tumoral injection of CMP-001. It is also highly recommended to continue to run additional fluids immediately following the CMP-001 injection, rather than waiting to initiate fluids when hypotension is detected. There is no waiting period between the end of prophylaxis and the start of CMP-001 intra-tumoral injection. All treatments given prophylactically pre-and post CMP-001 dosing should be recorded on the Prior and Concomitant Medications eCRF separately for each visit where it is given.

**IMPORTANT:** Subjects with a history of adrenal insufficiency are at increased risk for moderate to severe adverse events such as hypotension which may occur with 1-4 hours after injection. It is strongly recommended that these subjects receive stress dose steroids (eg. 50-100 mg hydrocortisone PO q 8 hours) prior to, or immediately after injection of CMP-001.

### 5.2.2.2 Timing of CMP-001 and nivolumab dosing

Initial study dose of nivolumab must be within 1 week of W1D1 (i.e., first CMP-001 injection). When CMP-001 and nivolumab dosing fall on the same day, it is recommended that CMP-001 dosing precede nivolumab dosing. There is no specified waiting period between the end of CMP-001 administration and the initiation of nivolumab infusion. When a study visit occurs where only nivolumab is given, pre-infusion vital signs should be collected and recorded on the eCRF.

### 5.2.2.3 Guidance of CMP-001 Injection

#### Intra-tumoral injections

Tumors selected for CMP-001 intra-tumoral injection should be at least 0.5cm in diameter and may be cutaneous, subcutaneous, and/or nodal tumors that are visible, palpable, or detectable by ultrasound guidance. Patients with visceral tumors are not candidates for this study. Patient candidates for CMP-001 injection may have more than one accessible tumor as a candidate for intra-tumoral injection.

- If 1 accessible tumor is present:
  - This should be selected as a candidate for intra-tumoral injection.
  - CMP-001 dose selection is outlined as in **Table 5.2.2.3-1**.
  - Total CMP-001 dose administered **should not exceed** 10mg/day.
- If >1 accessible tumors are present:
  - 1 or more accessible lesions can be injected (preferably all).
  - CMP-001 dose selection is outlined as in **Table 5.2.2.3-1**.
  - CMP-001 dose may be split at the discretion of the treating investigator (or designee).
  - Total CMP-001 dose administered across all tumors **should not exceed** 10mg/day.

**Table 5.2.2.3-1: CMP-001 Injection Volume Guidelines Based on Tumor Size (Doses 2-6 in Prime Phase)**

Dose Level	CMP-001 Dose (6mg/mL concentration)	Total Volume Injected
1	10mg	~2.0 mL
-1	7.5mg	~1.5 mL
-2	5mg	~1.0 mL
-3	2.5mg	~0.5 mL

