**Table 9.1-1: Product Descriptions**

Product Name and Potency	Dosage Form
CMP-001	Working concentration: 5.0 mg/mL. CMP-001 is a clear, colorless to pale yellow/brown liquid solution, essentially free of particles. Each single use vial contains 1.0 mL of CMP-001 (extractable volume of 1.0 mL = 5.0 mg dose) with a 0.1 mL overfill.

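### The CMP-001 injection table is headed 6 mg/mL, but its own volumes and the product description both correspond to 5.0 mg/mL; the passages must be reconciled

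*Combined protocol and SAP*

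**What the plan says.** Section 5.2.2 fixes the intra-tumoral dose: "Subsequent doses of CMP-001 administered during the Prime Phase (weeks 2-7) will be at 10mg administered intra-tumorally". For the amount to inject, Section 5.2.2.3 sends the site to Table 5.2.2.3-1, whether one tumor or several are accessible, and also relies on its volumes when judging at screening whether a tumor is large enough. Sections 5.2.2 and 5.2.2.4 use the same table for dose reductions. It is the only conversion from intra-tumoral dose to volume in the documents.

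The table has four dose levels: 10 mg in about 2.0 mL, 7.5 mg in about 1.5 mL, 5 mg in about 1.0 mL and 2.5 mg in about 0.5 mL. The dose column is headed "CMP-001 Dose (6mg/mL concentration)".

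Table 9.1-1 describes the product differently: "Working concentration: 5.0 mg/mL", and for the vial, "extractable volume of 1.0 mL = 5.0 mg dose".

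Section 5.2.2.3 also sets a limit: "Total CMP-001 dose administered across all tumors should not exceed 10mg/day".

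The table's title refers to tumor size and restricts the table to "Doses 2-6 in Prime Phase". Section 4.2.2 says that doses based on tumor size were explored in the initial safety run-in and that weeks 2 to 7 now use a fixed dose. The flow chart in Section 6.1 numbers the Prime Phase CMP-001 doses 1 to 7.

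**The concern.** Two parts of the protocol give different concentrations for the same drug, and one of them is the heading of the table that governs intra-tumoral dosing. No section describes a 6 mg/mL preparation or a dilution step that would explain the heading.

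Someone who reads a volume straight from a row never uses the heading. Someone who needs a volume that is not printed does. Section 5.2.2.3 allows a dose to be split across lesions at the investigator's discretion, so partial doses may have to be converted, and a stated concentration is what one would use for that. Intra-tumoral dosing is planned weekly in weeks 2 to 7, which is six injections per patient, all before the surgery at which pathologic response is read. Sections 4.1.4 and 5.2.2.7 report reactions resembling cytokine release, including severe hypotension, so doubt about how a volume relates to the daily limit should not remain in the protocol.

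**Working it through.** **Inputs.** Doses, listed volumes and the 6 mg/mL heading come from Table 5.2.2.3-1; the 5.0 mg/mL concentration and the 1.0 mL = 5.0 mg vial content from Table 9.1-1; the 10 mg/day limit from Section 5.2.2.3.

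**Formulas.** Implied concentration = dose / listed volume. Volume = dose / concentration. Delivered dose = volume x concentration.

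**Step 1: reproduce the table.** At the heading's 6 mg/mL the listed volumes do not reproduce: 10/6 = 1.67, 7.5/6 = 1.25, 5/6 = 0.83 and 2.5/6 = 0.42 mL. At 5 mg/mL all four do: 10/5 = 2.0, 7.5/5 = 1.5, 5/5 = 1.0 and 2.5/5 = 0.5 mL.

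**Step 2: the consequence of each combination.**

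| Dose (mg) | Listed volume (mL) | Implied mg/mL | Listed volume, 5.0 mg/mL vial (mg) | Volume calculated at 6 mg/mL (mL) | That volume, 5.0 mg/mL vial (mg) | Listed volume if product were 6 mg/mL (mg) |
|---|---|---|---|---|---|---|
| 10 | 2.0 | 5.0 | 10 | 1.67 | 8.33 | 12 |
| 7.5 | 1.5 | 5.0 | 7.5 | 1.25 | 6.25 | 9 |
| 5 | 1.0 | 5.0 | 5 | 0.83 | 4.17 | 6 |
| 2.5 | 0.5 | 5.0 | 2.5 | 0.42 | 2.08 | 3 |

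- Listed volume with the described product: 0% error in every row.
- Volume calculated from the heading, drawn from the described product: 5/6 - 1 = -16.7% in every row.
- Listed volume with a hypothetical 6 mg/mL product: 6/5 - 1 = +20% in every row. At the first dose level, 2.0 x 6 = 12 mg, which is 2 mg above the 10 mg/day limit.

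**Step 3: a split dose.** Take 10 mg divided equally between two lesions, 5 mg each. From the heading each share would be 5/6 = 0.83 mL. Drawn from a 5.0 mg/mL vial, each delivers 4.17 mg, and the two together 8.33 mg.

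**Step 4: can rounding or overfill explain the heading?** The volumes are marked as approximate. Rounding the 6 mg/mL volumes up to the next 0.5 mL does yield 2.0, 1.5, 1.0 and 0.5 mL, but those volumes at 6 mg/mL would still contain 20% more than the listed doses. The 0.1 mL overfill in Table 9.1-1 does not help either: it adds volume without changing concentration, and 1.1 mL x 5.0 mg/mL = 5.5 mg, not 6 mg.

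**Step 5: the title.** Weeks 2 to 7 are six weekly injections, numbered doses 2 to 7 in the flow chart. The title stops at dose 6 and mentions tumor size, although the table has no tumor-size column. The wording may be left over from the run-in; that is an inference.

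**The case against.** The strongest reply is that the table works in ordinary use. Staff pick a dose level, draw the printed volume from the product in Table 9.1-1, and the patient receives the printed dose. The shortfall requires someone to set aside the printed volume, calculate from the heading and miss the concentration on the vial and carton labels, which Section 9.2 requires. The excess requires a product that the documents do not describe. Section 9.4 leaves preparation to a pharmacy manual, which is not among the documents and may be clear.

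Most of this stands, and it limits the point. Four stronger readings might be inferred and are not supported:

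- *Every intra-tumoral dose is off by 17 to 20%.* The listed volumes with the described vials give the listed doses exactly.
- *The plan breaches its own daily limit.* With the described product, 2.0 mL holds 10 mg. The 12 mg figure is counterfactual on these documents.
- *Dose 7 has no volume.* The rows are dose levels, not injection numbers, and Section 5.2.2 sets the dose for weeks 2 to 7 and sends reductions in those weeks to this table. The title's range is an editorial inconsistency.
- *The primary objective is compromised because it names a dose.* Section 3.1 names none.

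What the reply does not remove is the contradiction itself. Labels and an unseen manual may prevent an error, but they do not make the protocol consistent, and dose splitting is a permitted route by which the heading could be used.

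**Conclusion.** The mismatch is certain: the heading disagrees with every row beneath it and with the product description. Its effect on delivered dose is conditional: none if listed volumes are drawn from 5.0 mg/mL vials, -16.7% if volumes are calculated from the heading and drawn from those vials, and +20% if the product were 6 mg/mL and listed volumes were used. These figures assume that the doses and volumes are as printed and that nothing outside the documents changes the concentration. How likely a preparation error is cannot be judged without the pharmacy manual. The matter has no bearing on the two-stage design, its error rates or the sample size. It should still be corrected, because the conflict sits in the operative dosing table and costs almost nothing to resolve. The title is a secondary, editorial matter. No view is taken on which concentration or dose is right.

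**What to change.** The sponsor should confirm the concentration and reconcile the heading of Table 5.2.2.3-1, its listed volumes and Table 9.1-1, so that concentration, dose and volume agree in every row. The pharmacy manual and the vial and carton labels should be checked against the result. In the same amendment, the table's title should be reconciled with Sections 4.2.2, 5.2.2 and 6.1 as to tumor size and the range of doses covered; how it is worded is for the sponsor.

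The cost is an edit to one table and its title, plus a check of the manual and labels. Visits, sample size and analyses do not change.

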#### Subcutaneous injections

CMP-001 should be injected using aseptic technique. Use of topical and/or local anesthetic is permitted. The injection may be given into any SC site in the body.

- Preferred Sites for Subcutaneous Injection
  - In principle, the injection may be given into any SC site in the body. Unsuitable sites for injection would include, for example, the palm of the hand or the sole of the foot.
  - The injection site should be within the area of lymphatic drainage associated with a site of metastatic disease or primary disease. For example, in a patient with a muscle or bone metastasis in the lower leg, the preferred SC injection site would be in the same leg, with the expectation that at least some of the CMP-001 will drain to lymph nodes that also contain tumor antigens. Likewise, in a patient with metastases in an upper lobe of the lung, a preferred SC injection site would be in the ipsilateral supraclavicular fossa, where the injection may activate pDC in the supraclavicular lymph nodes that also can drain the upper lung.
- Method of CMP-001 Subcutaneous Administration
  - Using standard aseptic technique, the needle is inserted into the subcutaneous tissue. After using gentle backward pressure on the syringe plunger to confirm extravascular location of the needle tip, the desired volume of CMP-001 is injected and the needle is withdrawn.

At Screening, the selected tumor(s) should be large enough to allow intratumoral injection of the intended volume of CMP-001 (**Table 5.2.2.3-1**). Initial administration of CMP-001 (W1D1) will be subcutaneous to allow for development of antibodies to the virus like particle which is necessary for uptake of CMP into the dendritic cell. Subsequent administrations of CMP-001 during the prime phase will be intra-tumoral. The same tumor(s) should be injected each week during therapy, if possible, except as outlined below to involuting tumors.

If the full volume cannot be injected within the tumor, then the remaining drug volume should be injected into a second accessible tumor, if present. If the full volume still cannot be administered into the tumor, peri-tumoral injection of any remaining volume is acceptable.

Following surgical resection, during the post-operative boost phase, CMP-001 will be administered subcutaneously at the resection site.

#### **5.2.2.4    CMP-001 Dose Modification**

CMP-001 will be dose-reduced in patients who develop CMP-001 related DLT and resume study therapy with Nivolumab/CMP-001 combination if Investigator determines that continued treatment with CMP-001 is in the subject's best interest. In this event, CMP-001 will be dose reduced as in **Table 5.2.2.3-1**.

[figure not shown]
CMP-001 will be withheld for CMP-001 related Grade 4 hematologic toxicities, non-hematological toxicity  $\geq$  Grade 3 including laboratory abnormalities, and severe or life-threatening AEs.

If CMP-001 is permanently discontinued for, subjects may continue to receive Nivolumab.

#### **5.2.2.5    Method of CMP-001 Administration**

Topical or local anesthesia may be given as appropriate in the Investigators' judgment. Using standard aseptic technique, the needle is inserted near the tumor periphery and is advanced into the tumor to the desired depth (usually to the needle hub, if the tumor size permits) while maintaining

gentle backward pressure on the syringe plunger to confirm extravascular location of the needle tip. The syringe and needle are then slowly withdrawn to within a few millimeters of the skin or tumor surface while maintaining gentle downward pressure on the plunger to inject the desired volume of CMP-001 along the needle track (**Figure 3, middle panel**). With the tip of the needle still within the skin, the syringe is then rotated by ~20-40° and the process of insertion and injection during needle withdrawal is repeated (**Figure 3, right panel**). Using this process, CMP-001 is injected along multiple tracks through a single insertion point as far as the radial reach of the needle allows within the tumor; two insertion points can be used if the tumor is larger than the radial reach of the needle and the intended CMP-001 volume cannot be delivered from a single insertion point. If gentle injection pressure along 5 needle tracks within the tumor has not succeeded in delivering the desired volume, then the remainder of the CMP-001 may be injected peri-tumorally, around the same lesion.

Essentially the same process is performed for cutaneous, subcutaneous, and nodal injections, but for deeper injections, the tip of the needle may be kept within the tumor and a longer needle may be used.

#### 5.2.2.6 Observation periods

During the Prime Phase, subjects must be observed for a period of at least four hours following each of the first three CMP-001 injections (W1D1, W2D1, W3D1) for signs and symptoms of reactions to the injection and other adverse events. Beginning with the fourth CMP-001 injection (W4D1) the observation period may be reduced to 1 hour following CMP-001 injection or per the discretion of the Investigator and agreement by Sponsor.

During the Boost Phase, subjects must be observed for a minimum of 1 hour following each CMP-001 injection for signs and symptoms of reactions to the injection and other adverse events. Observation periods longer than 1 hour during the Boost Phase should be based on the adverse event profile of the individual subject and be performed at the discretion of the Investigator.

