10. Has a history or current evidence of any condition, therapy, or laboratory abnormality that might confound the results of the trial, interfere with the subject's participation for the full duration of the trial, or is not in the best interest of the subject to participate, in the opinion of the treating investigator.
11. Has known psychiatric or substance abuse disorders that would interfere with cooperation with the requirements of the trial.
12. Is pregnant or breastfeeding, or expecting to conceive or father children within the projected duration of the trial, starting with the pre-screening or screening visit through 26 weeks after the last dose of trial treatment.
13. Has received prior therapy with an anti-PD-1, anti-PD-L1, anti-PD-L2, anti-CD137. Prior treatment with ipilimumab or interferon alfa is allowed. Patients with history of allergic or hypersensitivity reaction to interferon alfa or ipilimumab are also excluded.
14. Has a known history of Human Immunodeficiency Virus (HIV) (HIV 1/2 antibodies).
15. Has known active Hepatitis B (e.g., HBsAg reactive) or Hepatitis C (e.g., HCV RNA [qualitative] is detected. Patients with treated Hepatitis B/C with no evidence of active infection may be enrolled.

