#### 5.2.2.7 Management of CMP-001 toxicity

##### CMP-001 Associated Adverse Events

If subjects develop inflammation at the injection site this may be managed using cold compresses and/or acetaminophen or non-steroidal anti-inflammatory agents. If flu-like symptoms (i.e., fever, myalgia, and headache) arise, these may be managed using acetaminophen or non-steroidal anti-inflammatory agents.

[figure not shown]
It is expected that symptoms associated with a large release in cytokines at the time of injection could present 1-4 hours after the injection. These symptoms could include: fever, nausea/vomiting, chills/rigors, and hypotension. Subjects must remain in observation until all of these symptoms have resolved to  $\leq$  Grade 1. Refer to **Table 4.1.4-1** for current CMP-001 safety profile in the ongoing CMP-001-001 clinical study.

Subjects who experience a DLT will have dosing of CMP-001 withheld until the toxicity has returned to  $\leq$  Grade 1. If the Investigator determines that continued treatment with CMP-001 is in the subject's best interest, treatment may resume at a reduced dose of CMP-001. Only one dose reduction is allowed. Subjects who still experience DLTs at Dose Level-1 must come off study.

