#### CMP-001 Associated Cytokine Release-like Syndrome

As noted in **Section 4.2.2**, CMP-001 has been associated with symptoms associated with cytokine release. Most notable severe cases of hypotension have been noted, most often in subjects with a prior medical history of adrenal insufficiency secondary to ipilimumab. The backbone of the recommended treatment algorithm is the use of stress dose steroids and the IL6 antagonist tocilizumab (Maude et al. 2014; Lee et al. 2014; Tanaka et al. 2016; Brudno and Kochenderfer 2018).

The recommended algorithm for the treatment of symptoms associated with cytokine release below has been adapted for the treatment of cytokine release syndrome resulting from other immunotherapies such as CAR-T cell therapy (Lee et al. 2014) and is depicted in **Figure 4**. However, its effectiveness in treating symptoms associated with cytokine release resulting from CMP-001 has not been previously studied. The first line of treatment for hypotension unresponsive to supportive care such as fluids, is stress dose steroids as outlined below. Additional treatment measures include the use of drugs targeting specific cytokines believed to be involved in the development of cytokine release syndrome-induced hypotension. It is recommended that the treatment algorithm be implemented in subjects who present with acute hypotension following injection of CMP-001.

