**Study Calendar Notes:**

A≤4 weeks prior to first dose; magnetic resonance imaging (MRI)/computed tomography (CT) scans may be performed ≤4 weeks prior to first CMP-001 dose.

- During Screening, MRI brain with contrast (or CT equivalent) should be performed to exclude CNS metastatic disease. CNS imaging need not be repeated on study unless patient is symptomatic.

BEnd-of-treatment (EOT) assessments to be performed within 7 days following removal of subject from CMP-001 treatment. Removal of a subject from CMP-001 treatment is defined as the time in which the Investigator decides to discontinue CMP-001 treatment for a subject.

- Management of patients who develop unacceptable toxicity is defined in **Section 5.6**.
  - Patients who develop unacceptable toxicity deemed related to CMP-001 but not Nivolumab may continue Nivolumab after CMP-001 discontinuation for duration as defined in **Section 5.2.2.4**.
  - Patients who develop unacceptable toxicity deemed related to Nivolumab but not CMP-001 must discontinue both CMP-001 and Nivolumab.
- Patients who progress will undergo an optional biopsy to confirm progression at the time of RECIST v1.1 confirmed progression. This biopsy should be done within 14 days of RECIST v1.1 confirmed progression determination.

CCMP-001 is dosed weekly during the Prime Phase and q4 weekly during the Boost Phase of this study.

- Vital sign monitoring.
  - Weeks 1-3 (Prime Phase): vital signs are to be collected within 15 minutes prior to CMP-001 injection, and at 30 (±15) minute intervals for 4 hours following each of the first three CMP-001 injections.
  - Weeks 4-7 (Prime Phase): vital signs are to be collected within 15 minutes prior to CMP-001 injection, and at 30 (±15) minute intervals for 1 hour following each of the first three CMP-001 injections.
  - Boost Phase (all doses): vital signs are to be collected within 15 minutes prior to CMP-001 injection, and at 30 (±15) minute intervals for 1 hour following each of the first three CMP-001 injections.

DNivolumab dosing schedule is q2 weekly during the Prime Phase and either q2 weekly or q4 weekly during the Boost.

- During the Boost Phase of this study, Nivolumab can be dosed q2 or q4 weekly at the discretion of the treating investigator.
- If Nivolumab is dosed at q2 weeks during Boost phase, the patient will receive 23 doses of Nivolumab (doses 1-23; weeks 12-56).

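### From W4D1, observation after a 10 mg intra-tumoral CMP-001 injection may fall to 1 hour with no tolerance or risk condition, although the protocol puts cytokine-type symptoms at 1-4 hours

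*Combined protocol and SAP*

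**What the plan says.** Section 5.2.2.6 sets a minimum of 4 hours of observation after W1D1, W2D1 and W3D1. From the fourth injection "the observation period may be reduced to 1 hour following CMP-001 injection", or a period may be set by investigator discretion with sponsor agreement. No criterion based on earlier tolerance or medical history is attached. For the Boost Phase the same section sets a 1-hour minimum and adds: "Observation periods longer than 1 hour during the Boost Phase should be based on the adverse event profile of the individual subject".

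Note C of the Study Calendar Notes (Section 6.1) follows the same pattern. Its line beginning "Weeks 4-7 (Prime Phase): vital signs are to be collected within 15 minutes prior to CMP-001 injection" schedules readings every 30 (±15) minutes for 1 hour, with no exception for any patient.

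On timing, Section 5.2.2.7 expects that "symptoms associated with a large release in cytokines at the time of injection could present 1-4 hours after the injection", listing fever, nausea/vomiting, chills/rigors and hypotension. Patients must stay until these symptoms are Grade 1 or lower.

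On who is at risk, Section 5.2.2.1 singles out patients who have had adrenal insufficiency. It says that they "are at increased risk for moderate to severe adverse events such as hypotension which may occur with 1-4 hours after injection", and strongly recommends stress-dose steroids for them. It suggests prophylactic hydrocortisone "only for patients with prior G2-3 CRS-like reaction". The cytokine-release part of Section 5.2.2.7 says severe hypotension was seen "most often in subjects with a prior medical history of adrenal insufficiency secondary to ipilimumab". In Section 5.1.3, exclusion 13 states: "Prior treatment with ipilimumab or interferon alfa is allowed".

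**The concern.** The 4-hour rule for injections 1-3 matches the symptom window that the protocol describes. The 1-hour allowance from W4D1 does not, and nothing in the text says that the window narrows with later doses. A patient who had a Grade 2 reaction at W2D1 or W3D1 may be released after the same hour as a patient who had none.

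The groups most likely to be harmed can be identified in advance, because the protocol names them itself. It uses that knowledge to guide premedication and not to decide how long the patient is watched. All trial treatment is outpatient (Section 5.2.1.3), so the end of observation means leaving the clinic. What is at stake is hypotension or another cytokine-type reaction that begins after release in a patient known to be at higher risk.

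**Working it through.** The plan gives no figure to reproduce, so the check sets the provisions side by side and adds simple arithmetic.

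**Which doses are affected**
- Section 5.2.2: W1D1 is 5 mg subcutaneous; weeks 2-7 are 10 mg intra-tumoral unless reduced for side effects. That gives 6 planned intra-tumoral doses.
- Section 5.2.2.6: 4 hours is mandatory at W1D1, W2D1 and W3D1. Only 2 of these, W2D1 and W3D1, are intra-tumoral.
- One hour is permitted at W4D1, W5D1, W6D1 and W7D1: 4 doses, and 4/6 = 67% of the intra-tumoral doses. W4D1 is only the third intra-tumoral dose.

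**Overlap with the stated symptom window**
- The window runs from hour 1 to hour 4, which is 3 hours.
- Observation from 0 to 4 h covers 3 of 3 hours.
- Observation from 0 to 1 h covers 0 of 3 hours.

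**Vital signs at nominal 30-minute intervals (note C)**
- 4 hours: 240/30 = 8 post-injection sets.
- 1 hour: 60/30 = 2 sets. The difference is 6 sets per visit.

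**Whether another provision supplies the missing condition**

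| Provision | What it does | Why the gap remains |
|---|---|---|
| Discretion clause, 5.2.2.6 | Allows a longer stay | Requires it for no one; joined by *or*, it is an alternative and not a tolerance condition |
| Stay until Grade 1 or lower, 5.2.2.7 | Keeps symptomatic patients | Acts only on symptoms that begin before release |
| Dose-limiting toxicity rules, 5.2.2.4, 5.2.2.7 and 8.2 | Withhold, then reduce the dose | Non-laboratory toxicity generally qualifies from Grade 3; the response changes dose, not observation time |
| Prophylaxis, 5.2.2.1 | Lowers risk | Recommended, not required; sets no observation time |

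Together these allow the following course: Grade 2 hypotension at W3D1, no mandatory dose reduction, 10 mg at W4D1, release after 1 hour.

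**Whether the higher-risk patients can be in the trial**
Prior ipilimumab is allowed. Exclusion 7 lets patients on steroids of 10 mg daily or less enroll without stopping, and Section 5.2.2.1 gives instructions for adrenal insufficiency. Table 5.2.1.2-1 also lets both drugs continue during hypophysitis while hormone replacement is started. Adrenal insufficiency could therefore arise on study, which is a clinical inference.

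**What cannot be computed**
The number of patients reacting after hour 1 at W4D1-W7D1 is not derivable. Table 4.1.4-1 gives per-patient, any-dose rates without grade or onset time. For context only, related hypotension was 8/28 = 28.6% and fever 16/28 = 57.1% on the weekly schedule, pooled over 1 to 10 mg. The 3-weekly schedule (n=11) shows a dash for both, in a table limited to events seen in more than one subject.

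**The case against.** The strongest reply is that the rule is a permission. Nothing caps observation, an investigator may keep any patient for 4 hours, and note C does not forbid more readings. The proposal turns a bedside judgment into a mandate without a demonstrated harm rate, and the Grade 2 threshold is the proposal's own.

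The reply can point to more:
- Section 4.2.2 reports that the study's own safety run-in found no increase in adverse events at higher CMP-001 doses. Section 4.1.4 describes acute toxicity as mostly Grade 1-2 and generally short-lived.
- Grade 3 or higher reactors are already held and dose-reduced, and Section 8.7 provides weekly adverse event review.
- Exclusion 3 bars systemic steroids within 7 days of first dose, which conflicts with exclusion 7 and leaves it unsettled whether patients on replacement steroids can enter.
- Boost has the same 1-hour minimum and also relies on discretion, yet it would be left alone.
- The cytokine-release algorithm (Figure 4) is not visible and may address monitoring.

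Part of this stands. No harm rate can be shown. The contrast with Boost is one of wording: Boost tells the investigator to look at the patient's adverse event profile, but it too sets no enforceable trigger. The group left unprotected is mainly Grade 2 reactors and patients with adrenal insufficiency, and the documents do not say how many to expect.

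The central point survives. Discretion obliges no one to keep these patients longer, and the run-in finding concerns incidence by dose, not time of onset. Whatever the conflict between the two exclusions, Section 5.2.2.1 plainly anticipates patients with adrenal insufficiency.

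**Conclusion.** The point holds and should be fixed. For 4 of 6 planned 10 mg intra-tumoral doses, the plan permits an observation period that covers none of its own 1-4 hour symptom window, with no exception for the two groups it identifies as needing extra care.

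This rests on the visible text of Sections 5.2.2.1, 5.2.2.6 and 5.2.2.7 and note C, on 10 mg intra-tumoral being the usual dose at W4D1-W7D1, and on the 1-4 hour window applying to later doses, which the text does not exclude. It does not depend on any assumed event rate, on the Boost comparison, or on the remark in Section 4.1.4 about the third dose, which can be read either way. Confidence is medium, because the number of patients affected is unknown and careful investigators may already keep such patients longer.

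**What to change.** Replace the W4D1 sentence in Section 5.2.2.6 with:

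> At W4D1 through W7D1, observation may be reduced to 1 hour only for subjects with no history of adrenal insufficiency and no Grade 2 or higher cytokine-type reaction (fever, nausea/vomiting, chills/rigors, hypotension) after any earlier CMP-001 injection. All other subjects must be observed for at least 4 hours after each of these injections.

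In note C, weeks 4-7, schedule vital signs every 30 (±15) minutes for 1 hour, or for 4 hours in subjects who do not meet these criteria, after each injection. That line now refers to the first three injections, which cannot describe weeks 4-7, so it needs correcting in any case. The Boost rule can stay as written.

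The cost is two text edits. An affected patient spends up to 4 - 1 = 3 extra hours per visit and has 8 - 2 = 6 extra vital-sign sets, over at most 4 visits: up to 3 × 4 = 12 hours and 6 × 4 = 24 sets. Patients who tolerated earlier doses and have no adrenal insufficiency see no change. Dose, endpoint and sample size are untouched.
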